1.0 STUDY SUMMARY

Name of Sponsor: Takeda Development Center Americas, Inc, (TDC Americas) [name] [contact]	Compound: TAK-510
Study Identifier: TAK-510-1001	Phase: 1
Protocol Title: A Randomized, Double-Blind, Placebo-Controlled, Phase 1 Study to Evaluate the Safety, Tolerability, and Pharmacokinetics of TAK-510 in Healthy Subjects	
Study Design: This is a phase 1, randomized, double-blind, placebo-controlled study to evaluate the safety, tolerability, and pharmacokinetics (PK) of TAK-510 in healthy subjects. The study will consist of 3 parts: 
Part 1 is a first-in-human, randomized, double-blind, placebo-controlled, single rising dose (SRD) design to assess the safety, immunogenicity, tolerability, and PK of TAK-510 in healthy subjects. Up to 17 cohorts may be enrolled.Part 2 is a randomized, double-blind, placebo-controlled, multiple rising dose (MRD) design to assess the safety, immunogenicity, tolerability, and PK of TAK-510 in healthy subjects. Up to 8 cohorts may be tested in independent subject cohorts.Part 3 is a randomized, double-blind, placebo-controlled, multiple-dose, dose titration and redosing design to assess the safety, immunogenicity, tolerability, and PK of TAK-510 in healthy subjects. Up to 3 cohorts may be tested in independent subject cohorts using a dose titration design, followed by redosing with a single dose of study drug after a 7-day washout (168 hours after the previous dose). TAK-510 and matching placebo will be administered subcutaneously (SC). Safety will be assessed by monitoring for adverse events (AEs), vital signs, electrocardiogram (ECG)/telemetry, safety laboratory assessments after each dose, and immunogenicity. PK sampling times and scheme may vary based on emerging safety, tolerability and PK data, but the maximal number of samples or the maximum time point will not change. Subjects may not participate in more than 1 part or dosing cohort of the study.	
Study Primary Objective: 
Part 1:
To characterize the safety and tolerability of single SC doses of TAK-510 in healthy subjects.Part 2:
To characterize the safety and tolerability of multiple SC doses of TAK-510 in healthy subjects.Part 3:
To characterize the safety and tolerability of multiple SC dose regimens of TAK-510 that include titration from lower doses in healthy subjects. Secondary Objectives: 
Part 1:
To characterize the PK of TAK-510 in plasma following single SC doses in healthy subjects.To assess the immunogenicity of TAK-510 following single SC doses in healthy subjects.To characterize the PK of TAK-510 in urine following single SC doses in healthy subjects.Part 2:
To characterize the PK of TAK-510 in plasma following multiple SC doses in healthy subjects.To assess the immunogenicity of TAK-510 following multiple SC doses in healthy subjects.	

– To characterize the PK of TAK-510 in urine following multiple SC doses in healthy subjects. 
• Part 3:
– To characterize the safety and tolerability of single SC rechallenge doses of TAK-510 after a washout from multiple SC dose regimens that include titration from lower doses in healthy subjects.– To assess the immunogenicity of TAK-510 following multiple SC dose regimens that include titration from lower doses, washout, and redosing in healthy subjects.	

Study Subject Population: Healthy male and female (nonchildbearing potential only) subjects aged 18 to 55 years, inclusive, at screening. Body mass index ≥ 18 and ≤ 30.0 (kg/m^2) at the screening.
	
Planned Number of Subjects: 
Part 1: Up to approximately 136 subjects. Part 2: Up to approximately 64 subjects. Part 3: Up to approximately 24 subjects. Approximate values do not account for potential replacement of subjects who withdraw for nonsafety reasons.
	Planned Number of Sites: 
Up to 2 sites.

Dose Levels: 
Part 1: TAK-510 SRD: starting dose 5 μg Part 2: TAK-510 MRD: doses to be determined based on Part 1. Part 3: TAK-510 Dose Titration and Redosing: doses to be determined based on Parts 1 and 2.
	Route of Administration: 
Subcutaneous (SC)

Duration of Treatment: 
Part 1: 1 day. Part 2: 5 days. Part 3: 15 days (7 days plus 1 day after 7 days of washout.)
	Planned Study Duration: 
Approximately 57 days from screening (Day -28) until last follow-up visit (Day 29).

Main Criteria for Inclusion:
 
In order to be eligible for study participation, the subject must:
 
1. Understand the study procedures and agree to participate by providing written informed consent.2. Be willing and able to comply with all study procedures and restrictions.3. Be a healthy man or woman of nonchildbearing potential aged 18 to 55 years, inclusive, at the screening visit.4. Continuous nonsmoker who has not used nicotine- and tobacco-containing products for at least 3 months prior to dosing and throughout the study.5. Have a body mass index ≥ 18 and ≤ 30.0 (kg/m^2) at the screening visit.6. Be judged to be in good health (eg, no evidence of psychiatric, hepatic, renal, pulmonary, or cardiovascular disease) by the investigator, based on clinical evaluations including laboratory safety tests, medical history, physical examination, ECG, and vital sign measurements performed at the screening visit and before administration of the initial dose of study drug or invasive procedure.	

Main Criteria for Exclusion:
 
The subject must be excluded from participating in the study if:
 
• The subject has participated in another investigational study within 4 weeks (or based on local regulations) or within 5 half-lives of the investigational product before the screening visit. The 4-week or 5 half-lives window will be derived from the date of the last study dose and/or AE related to the study procedure in the previous study to the screening visit of the current study.• The subject has a history of significant multiple and/or severe allergies (eg, food, drug, latex allergy) or has had an anaphylactic reaction or significant intolerance to prescription or nonprescription drugs or food.	

- The subject has a positive pregnancy test or is lactating or breastfeeding.
- The subject is unable to refrain from or anticipates using all medications including herbal medicines beginning approximately 7 days before administration of the first dose of study drug, throughout the study until 2 days after discharge.
- The subject has a history or presence of:
 - 3 or more incidences of vasovagal syncope within the last 5 years prior to screening; or
 - A family history of unexplained sudden death or channelopathy; or
 - Brugada syndrome (ie, RBBB pattern with ST-elevation in leads V1-V3); or
 - Cardiovascular or cerebrovascular disease, such as cardiac valvulopathy, myocardial infarction, stroke, sick sinus syndrome, pulmonary congestion, symptomatic or significant cardiac arrhythmia, second-degree atrioventricular (AV) block type 2, third degree AV block, prolonged QT interval with Fridericia correction method (QTcF) interval, hypokalemia, hypomagnesemia, or conduction abnormalities; or
 - Risk factors for Torsade de Pointes (eg, heart failure, cardiomyopathy, or family history of Long QT Syndrome); or
 - Any clinically significant ECG findings or medical history including: long or short QTcF (over 450 msec or less than 360 msec), bifascicular block or QRS \geq 120 msec or PR interval $>$ 210 msec at screening or Day -1 pre-Hour 0; or
 - The subject has a documented history of sinus bradycardia (<45 beats per minute [bpm]) based upon vital signs assessments, sinoatrial block as evidenced on ECG or sinus pause \geq 3 seconds on ECG or predose telemetry.
- The subject has an average semirecumbent BP less than 90/60 mm Hg or greater than 140/90 mm Hg from screening to predose, inclusive. Any assessments on Day -1, where 2 consecutive time point values do not meet this criterion, must be discussed with the medical monitor for approval.
- The subject has an average HR <55 or >100 bpm from screening to predose, inclusive. Subjects with an average HR <55 bpm can be enrolled only with medical monitor approval. Any assessments after admission with an average HR <55 bpm, from Day -2 to predose (inclusive), will be left to the judgment of the investigator, unless HR is <50 bpm, which must be discussed with the medical monitor for approval.
- The subject has orthostatic hypotension defined as a decrease in systolic BP \geq 20 mm Hg or a decrease in diastolic BP \geq 10 mm Hg at approximately 3 minutes of standing when compared with BP from the semirecumbent position at screening to predose assessments, inclusive. In asymptomatic subjects, any assessments after screening that do not meet this criterion may be repeated after the subject has remained in the semirecumbent or supine position for 15 minutes. If the repeat assessment is exclusionary based on the above criterion, the subject will not be eligible. If the repeat assessment is not exclusionary, the subject will be eligible.
- The subject has postural orthostatic tachycardia, defined as an increase of >30 bpm or HR >120 bpm at approximately 3 minutes of standing, at screening to predose assessments, inclusive. Any assessments after screening that do not meet this criterion may be repeated with the subject remaining standing for up to a total of 5 minutes, provided that the subject remains asymptomatic. If the repeat assessment occurring within 5 minutes is exclusionary based on the above criterion, the subject will not be eligible. A confirmed orthostatic increase of >30 bpm, but <40 bpm, on 1 or more Day -1 assessments may not be considered exclusionary if not considered clinically significant by the investigator and the medical monitor. Such assessments must be discussed with the medical monitor prior to determination that the subject is eligible to proceed.

Main Criteria for Evaluation and Analyses:

The primary endpoint of the study is:

- Safety and tolerability as assessed through vital signs, ECG, laboratory assessments, and AEs.

The secondary endpoints will be assessed through evaluation of the following parameters:

- Part 1: plasma PK parameters for TAK-510
 - Maximum observed plasma concentration (C_{max}).
 - Area under the plasma concentration-time curve from time 0 to infinity (AUC_{∞}).
 - Area under the plasma concentration-time curve from time 0 to time of the last quantifiable concentration

(AUC_{last}).

- Time of first occurrence of C_{max} (t_{max}).
- Terminal disposition phase half-life ($t_{1/2z}$).
- Apparent clearance after extravascular administration (CL/F).
- Apparent volume of distribution during the terminal disposition phase after extravascular administration (V_z/F).
- Part 2: plasma PK parameters for TAK-510 on Day 1
 - C_{max} , t_{max} , and area under the plasma concentration-time curve during a dosing interval, where tau (τ) is the length of the dosing interval (AUC_τ).
- Part 2: plasma PK parameters for TAK-510 at steady state
 - AUC_τ , C_{max} , t_{max} , $t_{1/2z}$, CL/F, V_z/F , observed plasma concentration at the end of a dosing interval (C_{trough}), accumulation ratio based on AUC_τ ($R_{ac[AUC]}$), calculated as AUC_τ at steady state/ AUC_τ after a single dose, and accumulation ratio based on C_{max} ($R_{ac[Cmax]}$), calculated as C_{max} at steady state/ C_{max} after a single dose.
- Parts 1 and 2: urine PK parameters for TAK-510
 - Amount of drug excreted in urine from time 0 to time t (Ae_t).
 - Amount of drug excreted in urine from time 1 to time 2 (Ae_{t1-t2}).
 - Amount of drug excreted in urine during a dosing interval (τ) at steady state (Ae_τ).
 - Fraction of administered dose of drug excreted from urine from time 0 to time t ($f_{e,t}$).
 - Renal clearance (CL_R).
- Part 3:
 - Safety and tolerability of single SC rechallenge doses after a washout from multiple SC dose regimens of TAK-510 as assessed through vital signs, ECG, laboratory assessments, and AEs.
- All parts of the study:
 - Status of subject's antidrug antibody (ADA) assessment (ie, ADA-negative or ADA-positive, and low or high ADA titer).

Statistical Considerations:

Safety analyses will be based on the safety analysis set (defined as all subjects who are randomized and receive at least 1 dose of study treatment). No formal statistical tests or inference will be performed for safety analyses. All summary analyses will be performed by placebo, TAK-510 dose level (Parts 1 and 2 only)/dose regimen (Part 3 only), and TAK-510 overall within each part of the study separately. In particular, the number and percentage of subjects with at least 1 postdose value meeting the sponsor's markedly abnormal criteria for BP and HR will be provided. Placebo data will be pooled across cohorts within each part of the study. The same dose level (Parts 1 and 2 only)/dose regimen (Part 3 only) will be pooled across cohorts within each part of the study where appropriate. For Part 3 only, similar safety summary analyses (excluding ADA assessments) will be performed for the single dose after washout from multiple dose regimens of TAK-510 by placebo, TAK-510 single dose level after washout, and TAK-510 single dose overall after washout.

The plasma (all parts of the study) and urine (Parts 1 and 2 only) concentrations of TAK-510 will be summarized by dose level (Parts 1 and 2 only)/dose regimen (Part 3 only) at each scheduled sampling day/time within each part of the study separately, using descriptive statistics based on the PK analysis set (defined as all subjects who receive at least 1 dose of TAK-510 and have at least 1 measurable postdose plasma or urine concentration for TAK-510). The PK parameters of TAK-510 determined using a noncompartmental analysis approach will be summarized by dose level (Parts 1 and 2 only)/dose regimen (Part 3 only) of TAK-510, as appropriate, within each part of the study separately, using descriptive statistics based on the PK analysis set. Dose proportionality may be assessed graphically (log-transformed dose-normalized C_{max} and AUC versus dose) and by using a power model within each part of the study separately as data allow; no formal statistical comparisons will be conducted.

Sample Size Justification:

The selected sample sizes in Parts 1, 2, and 3 of the study are considered sufficient for evaluation of safety and tolerability of TAK-510 in healthy subjects. No formal statistical hypothesis testing is planned in Parts 1, 2, or 3. Therefore, no formal power calculations were performed in the determination of sample size for the study.

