^d All BP and pulse assessments should be made in duplicate, and the average of both assessments should be used to calculate the final result. The investigator can take a third measurement if there is inconsistency (ie, a difference >10 beats per minute in heart rate or a difference >10 mm Hg in systolic or diastolic BP) between assessments (see Section 9.2.4 for details). If 3 measurements are obtained, the final BP readout should be the average of the 2 more consistent assessments. On Day -1, vital signs will be time-matched (±5 minutes) to the Day 1 clock time (ie, time-matched baseline). At predose, vital signs will be measured within approximately 1 hour before the first dose. All BP and pulse assessments must be completed before PK blood sampling.

^e At least 24 hours of continuous telemetry monitoring will be conducted between check-in on Day -2 and predose on Day 1.

^f Predose time-matched telemetry extractions may take place between Day -2 and Day -1 in conjunction with the 24-hour predose continuous telemetry.

^g Dosing regimen for TAK-510/placebo will be determined based on data from Part 1.

^h Safety laboratory will include hematology, serum chemistry, and urinalysis parameters. During Part 2 (MRD), if a LFT (includes ALP, ALT, AST, GGT, or total bilirubin) is

CONFIDENTIAL

Table 3.b Part 2 for MRD Cohorts 13 to 17 and 26 to 28: Screening Through Day 9, Follow-Up, and ET

	Days													ET	
	Screening	-2 ^a	-1	Dosing					6	7	8	9 (Discharge)	Follow-up Visit Day 14 ±2 days	Follow-up Visit Day 29 ±3 days	
	-28 to -3			Pre dose	1	2	3	4	5						

elevated, a repeat test should be performed before the next dose of study drug is administered.

ⁱ If CK is elevated in an individual subject after dosing, additional serum samples for CK may be collected at the investigator's discretion. The medical monitor will be updated regularly on any findings of elevated CK and plans for continued monitoring.

^j Glucose finger stick will be performed at predose and ~1 hours postdose on each day.

^k Hepatitis panel, including HBsAg and anti-HCV.

^l Serum pregnancy tests for female subjects only.

^m An FSH level will be obtained to assess postmenopausal status.

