^d Follow-up doses should be given at the same time as on Day 1.

^e Safety laboratory will include hematology, serum chemistry, and urinalysis parameters. During Part 2 (MRD), if a LFT is elevated, a repeat test should be performed before the next dose of study drug is administered.

^f Safety laboratory assessments (including hematology, serum chemistry, and urinalysis parameters) will be performed on Day 2 and Day 4.

^g Sampling for LFTs will be performed on Day 3.

^h Blood samples for PK may be drawn 10 minutes before dosing.

ⁱ Subjects will be confined.

3.2.4 Part 2 for MRD Day 5 Through Day 9 Assessments, Follow-Up, and Early Termination

Table 3.e Part 2 for MRD Day 5 Through Day 9 Assessments, Follow-Up, and ET

	Scheduled Time															ET					
	Day 5 (Hours)														Day 6	Day 7	Day 8	Day 9 (Discharge)	Follow-up Visit Day 14 ±2 days	Follow-up Visit Day 29 ±3 days	
	Pre dose	0	0.5	1	2	3	4	5	7	10	12	16	24	48	72	96					
Prior and concomitant medications		X-----Continuous review-----X																			
Clinic Procedures/Assessments																					
Full physical examination													X ^a			X ^a			X		
Temperature and respiratory rate	X				X		X						X			X			X		
BP and pulse ^b	X		X	X	X	X	X	X	X	X	X	X			X	X	X	X			
Standing BP and pulse ^c	X		X		X		X		X	X			X					X			
TAK-510/placebo administration ^d		X																			
12-lead ECGs															X						
ECG telemetry (12-lead)	X												X								
Telemetry extraction	X		X	X	X	X	X	X	X	X	X	X									
AE monitoring	X												Continuous					X			
Laboratory Procedures/Assessments																					
Safety laboratory collection ^e													X			X	X	X	X		
Serum sample for CK ^f																X			X		
Glucose finger stick	X					X															
βhCG (pregnancy) test ^g															X				X		

CONFIDENTIAL

Table 3.e Part 2 for MRD Day 5 Through Day 9 Assessments, Follow-Up, and ET

	Scheduled Time															ET					
	Day 5 (Hours)														Day 6	Day 7	Day 8	Day 9 (Discharge)	Follow-up Visit Day 14 ±2 days	Follow-up Visit Day 29 ±3 days	
	Pre dose	0	0.5	1	2	3	4	5	7	10	12	16	24	48	72	96					
PK Evaluations																					
Plasma sample for TAK-510 PK	X ^h		X	X	X	X	X	X	X	X	X	X	X	X	X	X			X		
Plasma sample for metID	X ^h		X		X	X		X		X		X		X					X		
Urine sample for TAK-510 PK ⁱ			X				X		X		X										
Immunogenicity and Biomarkers																					
Serum sample for immunogenicity ^j														X			X	X	X		
Blood sample for DNA (optional) ^k																X			X		

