Other																					
Confinement ^m	X-----													X							

ADA: antidrug antibodies; AE: adverse event; β hCG: beta human chorionic gonadotropin; BP: blood pressure; CK: creatine kinase; ECG: electrocardiogram; ET: early termination; metID: metabolite identification; PK: pharmacokinetic.

^a Physical examination at the indicated visit will be symptom-driven.

^b All BP and pulse assessments should be made in duplicate, and the average of both assessments should be used to calculate the final result. The investigator can take a third measurement if there is inconsistency (ie, a difference >10 beats per minute in heart rate or a difference >10 mm Hg in systolic or diastolic BP) between assessments (see Section 9.2.4 for details). If 3 measurements are obtained, the final BP readout should be the average of the 2 more consistent assessments. At predose, vital signs will be measured within approximately 1 hour before the first dose. All BP and pulse assessments must be completed before PK blood sampling.

^c For standing BP and pulse assessment, a BP and pulse assessment will be performed after the duplicate semirecumbent assessment has been completed. The subject should stand still for approximately 3 minutes before this assessment. Standing assessments must not be performed if semirecumbent systolic BP is <85 mm Hg or if the subject presents with signs or symptoms suggestive of postural hypotension after standing (eg, lightheadedness or dizziness, nausea, blurry vision, etc.).

^d Follow-up doses should be given at the same time as those given on Day 1.

CONFIDENTIAL

Table 3.e Part 2 for MRD Day 5 Through Day 9 Assessments, Follow-Up, and ET

	Scheduled Time														ET		
	Day 5 (Hours)												Day 6	Day 7	Day 8	Follow-up Visit Day 14 ±2 days	Follow-up Visit Day 29 ±3 days
	Pre dose	0	0.5	1	2	3	4	5	7	10	12	16	24	48	72	96	

^e Safety laboratory will include hematology, serum chemistry, and urinalysis parameters. Additional assessments may be collected at the investigator's discretion.

^f If CK is elevated in an individual subject after dosing, additional serum samples for CK may be collected at the investigator's discretion. The medical monitor will be updated regularly on any findings of elevated CK and plans for continued monitoring.

^g Serum pregnancy tests for female subjects only.

^h Blood samples for PK and metID may be drawn 10 minutes before dosing.

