^d Follow-up doses should be given at the same time as on Day 1.

^e Telemetry extractions will be performed only on day(s) when the dose has changed from the previous day, and only if PK samples are collected at the given time point.

^f Safety laboratory will include hematology, serum chemistry, and urinalysis parameters. During Part 3, if a LFT is elevated, a repeat test should be performed before the next dose of study drug is administered.

^g Safety laboratory assessments (including hematology, serum chemistry, and urinalysis parameters) will be performed on Day 2, Day 4, and Day 6.

^h Samples for LFTs will be performed on Day 3 and Day 5.

ⁱ Blood samples for PK may be drawn 10 minutes before dosing.

^j Samples will be collected only on day(s) when the dose has changed from the previous day. Sampling times may change based on emerging data from Part 1.

^k Subjects will be confined.

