6.0 STUDY DESIGN AND DESCRIPTION

6.1 Study Design

6.1.1 Overall Study Design

This is a phase 1, randomized, double-blind, placebo-controlled study to evaluate the safety, tolerability, and PK of TAK-510 in healthy subjects.

The study will consist of 3 parts:

- Part 1 is a FIH, randomized, double-blind, placebo-controlled, SRD design to assess the safety, immunogenicity, tolerability, and PK of TAK-510 in healthy subjects. Up to 17 cohorts may be enrolled.
- Part 2 is a randomized, double-blind, placebo-controlled, MRD design to assess the safety, immunogenicity, tolerability, and PK of TAK-510 in healthy subjects. Up to 8 cohorts may be tested in independent subject cohorts.
- Part 3 is a randomized, double-blind, placebo-controlled, multiple-dose, dose titration and redosing design to assess the safety, immunogenicity, tolerability, and PK of TAK-510 in healthy subjects. Up to 3 cohorts may be tested in independent subject cohorts using a dose titration design, followed by redosing with a single dose of study drug after a 7-day washout (168 hours after the previous dose).

TAK-510 and matching placebo will be administered SC. Safety will be assessed by monitoring for AEs, vital signs, ECG/telemetry, safety laboratory assessments after each dose, and

CONFIDENTIAL

immunogenicity. PK sampling times and scheme may vary based on emerging safety, tolerability and PK data, but the maximal number of samples or the maximum time point will not change. Subjects may not participate in more than 1 part or dosing cohort of the study.

An overview of treatment cohorts is outlined in [Table 6.a](#). A schematic of the study design is presented in Section [2.0](#). The schedule of study procedures is presented in Section [3.0](#).

Table 6.a Overview of Treatment Cohorts

Cohort	Regimen	Treatment	
Part 1			
1	SRD ^a	TAK-510	
2		6	2
3		6	2
4		6	2
5		6	2
6		6	2
7		6	2
8		6	2
9		6	2
10		6	2
11		6	2
12		6	2
21		6	2
22		6	2
23		6	2
24		6	2
25		6	2
Part 2			
13	MRD	TAK-510	
14		6	2
15		6	2
16		6	2
17		6	2
26		6	2
27		6	2
28		6	2
Part 3			
18	Dose Titration, Washout, Redosing	TAK-510	
19		6	2
20		6	2

MRD: multiple rising dose; SRD: single rising dose.

^a Up to 17 doses may be explored with a maximum escalation factor between cohorts of 5-fold at lower exposures and 2-fold at high exposures.

6.1.2 Part 1: SRD Cohorts 1 to 12 and 21 to 25

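### Part 2 schedules no safety panel or LFT between the Day 4 and Day 5 doses, although Sections 1.0 and 6.1.1 say safety laboratory tests follow each dose

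*Protocol*

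**What the plan says.** Section 1.0 lists "safety laboratory assessments after each dose, and immunogenicity" among the ways safety is assessed. Section 6.1.1 repeats it: "ECG/telemetry, safety laboratory assessments after each dose, and".

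The Part 2 schedule is narrower. Dosing is once daily on Days 1 to 5. For Days 2 to 4, Table 3.d puts the laboratory marks in the predose column, and its footnotes f and g fix the days: "Safety laboratory assessments (including hematology, serum chemistry, and urinalysis parameters) will be performed on Day 2 and Day 4", and "Sampling for LFTs will be performed on Day 3". Table 3.e, which runs from Day 5, has its first safety laboratory mark in the 24-hour (Day 6) column. It has no mark at Day 5 predose and no LFT row. The overall Table 3.b agrees, with panels on Days 1, 2, 4, 6 and 9, LFTs on Day 3 and nothing on Day 5.

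The rule linking liver results to dosing is in Table 3.d footnote e: "if a LFT is elevated, a repeat test should be performed before the next dose of study drug is administered". Table 3.b footnote h states the same rule for Part 2 as a whole. Section 9.2.9.2 adds, for Parts 2 and 3, an ALT/AST repeat before the next dose when ALT or AST exceeds 3 x ULN or total bilirubin exceeds 2 x ULN. If ALT or AST stays above 3 x ULN, the medical monitor is contacted and stopping study drug is among the options.

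For Part 3, Table 3.h footnote g says: "Safety laboratory assessments (including hematology, serum chemistry, and urinalysis parameters) will be performed on Day 2, Day 4, and Day 6". Footnote h puts LFTs on Days 3 and 5, and Table 3.i adds a panel at Day 7 predose.

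**The concern.** Section 4.3 names elevated liver enzymes as a potential risk of TAK-510. The repeat rules can protect a subject from a further dose only if a liver result exists before that dose. The Day 4 sample is drawn before dose 4 and so says nothing about that dose's effect. If a subject's LFTs are normal through Day 4 and first rise after dose 4 without symptoms, no scheduled test shows it before dose 5, and the rules then have no dose left to act on.

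Part 2 otherwise alternates panel, LFTs, panel on Days 2, 3 and 4, then stops before the last dose. Part 3 continues the alternation through its last daily dose. No reason is given for the difference, which looks more like an omission than a choice. The subjects are healthy volunteers for whom Section 4.3 expects no clinical benefit.

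**Working it through.** No power or sample size figure is involved. The check counts, for each dose, the scheduled panels or LFTs that fall after it and no later than the next predose time.

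**Inputs.** Part 2 dosing days: Section 6.1.3 and Table 3.b. Part 2 laboratory marks: Tables 3.b to 3.e. Part 3 marks: Tables 3.h and 3.i. By Table 3.d footnote a, the Day 4 24-hour sample is the Day 5 predose sample, so an empty cell there is one missing sample.

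**Part 2, five daily doses**

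| Dose | Scheduled before the next dose (dose 5: at 24 h) |
|---|---|
| 1 | Safety laboratory at 4 h; panel at Day 2 predose |
| 2 | LFTs at Day 3 predose |
| 3 | Panel at Day 4 predose |
| 4 | None |
| 5 | Panel at 24 h (Day 6) |

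- Doses followed by a panel or LFTs: 4 of 5, against the stated *each dose*.
- Between-dose intervals: 5 - 1 = 4. Without a liver test: 1 of 4.
- Liver-test gap: Day 4 predose to 24 h after the Day 5 dose = 24 + 24 = 48 h, containing doses 4 and 5.

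**Part 3, seven daily doses.** Predose samples: panel (Day 2), LFTs (Day 3), panel (Day 4), LFTs (Day 5), panel (Day 6), panel (Day 7). Intervals: 7 - 1 = 6. Without a liver test: 0 of 6. Gaps between daily doses are 24 h. From Day 7 predose to the Day 8 discharge sample the gap is 24 to 30 h and contains one dose.

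**With a Day 5 predose LFT in Part 2.** Coverage becomes 5 of 5 doses and the 48 h gap splits into two of about 24 h. First scheduled detection of a rise after dose 4 moves from about 48 h after that dose (Day 6) to about 24 h or a little less, before dose 5.

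**Subjects.** 8 cohorts x 8 = 64; 8 x 6 = 48 on TAK-510 and 8 x 2 = 16 on placebo.

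**Blood volume.** Section 4.3 gives about 505 mL for Part 2 and a limit of 575 mL. The protocol states no tube volume. Assuming 2 to 10 mL, the total becomes 505 + 2 = 507 to 505 + 10 = 515 mL, still below 575 mL.

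**The case against.** The sentence in Sections 1.0 and 6.1.1 is a one-line overview. It says after each dose, not before the next one, and the Day 6 panel does come after dose 4. Section 6.1.1 also refers to Section 3.0 for the schedule. No rule requires a liver test between every pair of doses, and Part 2 need not copy Part 3. The protocol sets no time for reviewing a predose result before that day's dose, so a Day 5 sample might inform nothing. Subjects are confined to Day 9, unscheduled tests are allowed (Section 9.0), and Part 2 daily exposure may not exceed what Part 1 showed to be tolerated.

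The reading that lets one Day 6 panel serve both doses 4 and 5 is strained, and it still leaves dose 5 given with no liver result reflecting dose 4. Discretionary testing does not help, because an asymptomatic first rise prompts no test. The timing objection stands: an extra mark in the table is useful only if the result is available before dosing, so the fix must set the time. The remarks on limited consequence also stand.

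A reader might infer three stronger points that the documents do not support.

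- *Table 3.e lacks the repeat rule.* Its footnote e reads "Safety laboratory will include hematology, serum chemistry, and urinalysis parameters. Additional assessments may be collected at the" investigator's discretion, and does not mention repeating an elevated LFT. This is no defect. As the table stands, its first panel comes after the last dose. Table 3.b footnote h ("if a LFT (includes ALP, ALT, AST, GGT, or total bilirubin) is" elevated) and Section 9.2.9.2 already apply the repeat rules across Part 2.
- *Renal monitoring is also weaker in Part 2.* Creatinine comes only with the full panel. It is absent from 2 of 4 intervals in Part 2 and 2 of 6 in Part 3, and the longest gap is 48 h in both. There is no contrast in that gap on which to base a finding.
- *Dose escalation is compromised.* Section 6.1.3 asks for laboratory results at least 24 h after the last dose in the cohort, which the Day 6 panel supplies. It also still feeds the Section 6.2.2 criteria.

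**Conclusion.** The point holds as a mismatch between the stated monitoring and the Part 2 schedule, with a small safety consequence. One of four between-dose intervals in Part 2 has no liver test, against none of six in Part 3. A subject whose first LFT rise follows dose 4 without symptoms would receive one further dose, and the rise would be detected about 24 h later than a Day 5 sample would allow.

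This rests on two things. The table marks are read by column position; Tables 3.b, 3.d and 3.e agree on them. And the gain at dose 5 depends on the Day 5 result being available before dosing, which the protocol does not now arrange. The change is worth making because it is cheap and brings the schedule into line with the stated design. The gap does not undermine Part 2 or its escalation decisions.

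**What to change.** 1. Add a Day 5 predose LFT sample to Tables 3.b and 3.e.
2. Give it its own nominal time, early enough for the result to be reviewed before dose 5. It should not share the PK draw, which Table 3.e footnote h allows 10 minutes before dosing. Section 9.2.10 holds chemistry samples to within 10 minutes of nominal, so the earlier time has to be written into the table.
3. Update the Part 2 blood volumes in Section 4.3.
4. Reword Sections 1.0 and 6.1.1 to say that a safety panel or LFTs follow each dose. The wording matters because Table 3.d footnote e defines the safety laboratory as hematology, chemistry and urinalysis, which an LFT-only day does not meet.

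No new repeat rule is needed.

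The cost is one small tube per Part 2 subject, possibly as a separate earlier draw. Subjects are already confined and fasting overnight before the Day 5 dose (Section 7.4.1.2). If Day 5 is the day of maximum sampling, the single-day figure of about 147 mL becomes about 149 to 157 mL under the same 2 to 10 mL assumption. The rewording costs nothing.
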